Statistical Methodology	Efficacy of the study will be measured by estimating the objective response rate (CR, PR) in the breast and/or the axillary lymph nodes or determining if the combination of Abemaciclib and Fulvestrant increases the percentage of patients who undergo breast conserving surgery. The latter will be measured by constructing 95% CI. We plan to use survival analysis methods such as Kaplan-Meier estimates of survival probability for univariate analysis and log rank tests in order to evaluate differences among distinct patient characteristics such as age group for recurrence or disease-free survival. For multivariate analysis we plan to use the Cox proportional hazards model in order to examine survival adjusted for a number of covariates. Safety and toxicity will be examined by the incidence of treatment-emergent, treatment-related adverse events (TRAEs), and serious adverse events (SAE). Consequently, side effects and adherence to the protocol will be closely monitored throughout the duration of the study. Interim analyses will be performed to assess the side effects. Contingency tables will be constructed to compare the proportion of patients with side effects by study characteristics (e.g. age, race ethnicity and other clinical and epidemiologic characteristics). Distributions of all data items will be generated and examined for the presence of outliers. This will be to assess the general form of the distributions, and to compute measures of central tendency and variability. Trellis graphics will be used for data display including histograms, boxplots, and Q-Q normal plots. In addition, we plan to examine if genomic analysis of patient-matched breast tissue samples and serial mutational tracking of circulating tumor DNA can identify new mechanisms of endocrine resistance and the way Abemaciclib overcomes this resistance. For the analyses of matched pair tissue data, we will use paired t tests or Wilcoxon sign rank statistical analysis in order to test differences in recurrent and treated breast tissue. We plan to measure absolute values and changes in circulating tumor DNA and correlate them with endocrine resistance. If serial monitoring of ctDNA can provide markers of resistance, we will quantify endocrine resistance as a composite outcome that will be computed as dichotomous variable if it happens (yes or no) and at what time interval during the study. We will start by using frequency table analysis to examine the relationship between resistance or sensitivity and specific mutations.

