7.0 ADVERSE EVENTS

Adverse event (AE) monitoring and reporting is a routine part of every clinical trial. The investigator will use CTCAE v 5.0 to assign AE severity grades. Investigators are responsible for monitoring the safety of patients who have entered this study and for alerting Eli Lilly Pharmaceuticals to any event that seems unusual, even if this event may be considered an unanticipated benefit to the patient.

The investigator is responsible for the appropriate medical care of patients during the study.

The investigator remains responsible for following, through an appropriate health care option, AEs that are serious or otherwise medically important, considered related to the investigational product or the study, or that caused the patient to discontinue the investigational product before completing the study. The patient should be followed until the event resolves, stabilizes with appropriate diagnostic evaluation, or is otherwise explained. The frequency of follow-up evaluations of the AE is left to the discretion of the investigator.

Lack of drug effect is not an AE in clinical trials, because the purpose of the clinical trial is to establish drug effect.

After the ICF is signed, study site personnel will record via OnCore eCRF the occurrence and nature of each patient's preexisting conditions, including clinically significant signs and symptoms of the disease under treatment in the study. In addition, site personnel will record any change in the condition(s) and any new conditions as AEs. Investigators should record their assessment of the potential relatedness of each AE to protocol procedure, investigational product, via OnCore eCRF.

The investigator will interpret and document whether or not an AE has a reasonable possibility of being related to study treatment taking into account the disease, concomitant treatment or pathologies.

A "reasonable possibility" means that there is a cause and effect relationship between the investigational product, study device and/or study procedure and the AE.

Planned surgeries and nonsurgical interventions should not be reported as AEs unless the underlying medical condition has worsened during the course of the study.

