Table X1 presents sample size of Simon's two-stage design. Where n is the total number of subjects, n₁ is the number of subjects accrued during stage 1, if r₁ or fewer responses are observed during stage 1, the trial is stopped early for futility. If r₂ or fewer responses are observed by the end of stage two, then no further investigation of the drug is warranted, EN₀ is the expected sample size for the trial when response rate is p₀ and p₀ and p₁ are the response probabilities under the null and under the alternative hypothesis. Thus, the null hypothesis that the true response rate is 10% will be tested against a one-sided alternative. In the first stage, 10 patients will be accrued. If there are one or fewer responses in these 10 patients, the study will be stopped. Otherwise, 19 additional patients will be accrued for 29. The null hypothesis will be rejected if 6 or more responses are observed in 29 patients. This design will yield a type I error rate of 0.0471 and power of 80% when the true response rate is 0.3. Thus, we anticipate recruiting 29 evaluable participants with at least 10 in stage 1. (Simon 1984, Jung et al 2004) (16, 17). Given the sample size of 30 participants, power in the statistical design will be low for the secondary and exploratory endpoints. Efficacy of the study as measured by estimating the objective response rate in the breast and/or the axillary lymph nodes or determining if the combination of Abemaciclib and Fulvestrant increases the percentage of patients who undergo breast conserving surgery will be measured by constructing 95% CI. We plan to use survival analysis methods such as Kaplan- Meier estimates of survival probability for univariate analysis and log rank tests in order to test for differences among different patient characteristics such as age group for recurrence or disease-free survival. For multivariate analysis in order to examine survival adjusted for a number of covariates we plan to use the Cox proportional hazards model. In order to examine the safety and toxicity which will be determined by the incidence of treatment-emergent, treatment-related adverse events (TRAEs), and serious adverse events (SAE) we plan to monitor side effects and adherence to the protocol throughout the duration of the study. Interim analyses will be performed to assess the presence of side effects. Contingency tables will be constructed to compare the proportion of patients with side effects by study characteristics as age, race ethnicity and other clinical and epidemiologic characteristics. Distributions of all data items will be generated and examined for the presence of outliers, in order to assess the general form of the distributions, and to compute measures of central tendency and variability. Trellis graphics will be used for data display including histograms, boxplots, and Q-Q normal plots. In addition, we plan to examine if genomic analysis of patient matched breast tissue samples and serial mutational tracking of circulating tumor DNA can identify new mechanisms of endocrine resistance and how

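### Age is grouped and toxicity is counted as present or absent in the secondary comparisons, although age and CTCAE grade are both recorded; using them as measured is a near-free improvement

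*Combined protocol and SAP*

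**What the plan says.** Section 10.2 names two univariate methods for relating outcomes to patient characteristics.

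- For time to recurrence, it plans Kaplan-Meier estimates with "log rank tests in order to test for differences among different patient characteristics such as age group for recurrence or disease-free survival".
- For toxicity: "Contingency tables will be constructed to compare the proportion of patients with side effects by study characteristics as age", followed by race/ethnicity and other clinical and epidemiologic characteristics.

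The Statistical Methodology row of the Study Summary repeats both. Neither place gives the number of age groups, their limits, or the grade at which a side effect counts.

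The finer data exist. Section 5.1.4 collects age, and Section 7.0 states: "The investigator will use CTCAE v 5.0 to assign AE severity grades". Section 10.2 also plans a multivariable Cox model without naming its covariates or the form of age. It summarises safety as the incidence of treatment-related and serious adverse events, and concedes low power for secondary and exploratory endpoints.

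**The concern.** Grouping a measured variable treats everyone within a group as alike. With about 30 patients that loss matters, and nothing is gained in return beyond a simple display.

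The toxicity tables may lose information twice, because age is grouped and an ordinal grade becomes yes or no. Section 8.1 lists ten common side effects of abemaciclib. If almost every patient has at least one, the yes/no margin is nearly constant and the table has little left to compare. A real age gradient in severity could then pass as no difference. Admitted low power is a reason to keep the information already in hand. Unstated cut points could also be chosen after the data are seen.

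**Working it through.** **The plan's own figure.** Section 10.2 gives a Simon design for pCR with null rate 0.10 and alternative 0.30, stopping at 1 or fewer of 10 and rejecting at 6 or more of 29. Early stopping under the null is 0.9^10 + 10 × 0.1 × 0.9^9 = 0.7361, and the expected size is 10 + (1 − 0.7361) × 19 = 15.01. Exact two-stage binomial sums give type I error 0.0471 and power 0.8051. All match the plan, and none involves age or grade, so the primary test is untouched.

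**Numbers of patients.** Recurrence is timed from surgery (Section 6.2.7); I take 29. Safety covers everyone given a dose (Section 6.3), about 30 / (1 − 0.05) = 31.6, so 32.

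**Information lost by grouping age.** Assume roughly normal age and a small linear effect. One cut at quantile q keeps φ(z_q)² / [q(1 − q)].

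- Median: 0.3989² / 0.25 = 0.637. The loss is 36%, and 29 patients act like 29 × 0.637 = 18.5.
- 25/75 split: 54% kept. 20/80: 49%. 10/90: 34%.
- Three equal groups keep 79% and four keep 86%, a loss of 21% and 14%. An unordered log-rank test also spreads this over two or three degrees of freedom, so its power falls somewhat further.
- If age were uniform, a median cut would keep 75%.

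**Information lost by scoring toxicity yes/no.** Under proportional odds, a yes/no score with event proportion p keeps p(1 − p) / [(1 − Σp_k³)/3] of what the grade carries. Halving age as well multiplies this by about 0.637. The grade distributions are assumed.

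| Any side effect | Proportions at grades 0 to 4 | Kept by yes/no | Kept with age also halved |
|---|---|---|---|
| 30% | 0.70, 0.12, 0.10, 0.06, 0.02 | 96% | 61% |
| 50% | 0.50, 0.20, 0.15, 0.10, 0.05 | 87% | 55% |
| 70% | 0.30, 0.25, 0.25, 0.15, 0.05 | 67% | 43% |
| 80% | 0.20, 0.25, 0.30, 0.20, 0.05 | 51% | 33% |
| 90% | 0.10, 0.20, 0.35, 0.28, 0.07 | 29% | 19% |
| 95% | 0.05, 0.20, 0.35, 0.32, 0.08 | 16% | 10% |

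For the 90% row: Σp_k³ = 0.0742, (1 − 0.0742)/3 = 0.3086, and 0.09 / 0.3086 = 0.29.

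**Simulated power for toxicity** (n = 29, two-sided 5%, 3,000 runs, assumed cumulative odds ratio 2.7 per SD of age):

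| Any side effect | Fisher, any grade by median age | Fisher, grade ≥ 3 by median age | Spearman, worst grade on age |
|---|---|---|---|
| 50% | 34% | 23% | 69% |
| 70% | 29% | 27% | 74% |
| 90% | 9% | 32% | 74% |
| 95% | 2% | 34% | 74% |

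With no age effect, Spearman rejects in 4 to 6% of runs and the Fisher tests in 3% or fewer. At odds ratio 2 and any-effect rates of 80 to 98%, the any-grade table has 12% power or less, against 44 to 48%. With 32 patients and odds ratio 3, the contrast is 0 to 28% against 83 to 85%.

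**Simulated power for recurrence** (n = 29, four-year accrual, end at five years, surgery assumed at six months, assumed recurrence hazards 0.1, 0.2 and 0.3 per year):

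| Events, about | HR per SD | Log-rank, median split | Cox score, continuous age | Gain, points |
|---|---|---|---|---|
| 7 | 2 | 25% | 40% | 15 |
| 12 | 2 | 38% | 57% | 19 |
| 15 | 2 | 45% | 66% | 21 |
| 7 | 1.5 | 12.5% | 17.3% | 4.8 |
| 12 | 1.5 | 17.2% | 24.2% | 7.0 |
| 15 | 1.5 | 20.3% | 30.2% | 9.9 |

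A second run gave gains of 17, 17 and 22 points at HR 2 and 4, 7 and 11 at HR 1.5, which agrees within simulation error. Both tests reject about 5% of the time under the null.

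**The case against.** Several objections have force.

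- A reader might infer that the plan throws away most of the usable information. For age alone the documents do not support that. No cut point is given, sensible groupings keep 64 to 86%, and a single cut loses more than half only if it is about as uneven as 20/80 or worse.
- A reader might also infer that the toxicity tables are bound to show nothing. That requires side effects to mean any event of any grade. The preceding sentence in Section 10.2 speaks of treatment-related and serious events, and a separate table per side effect is an equally fair reading. Section 8.2 does give some fulvestrant rates: hot flashes 23.5%, urinary infection up to 9.3%, joint disorders 9.3%. Abemaciclib effects are called common without rates. With continuous age and 32 patients, using grade instead of yes/no adds only 0 to 1 point of power for an event at 23.5%, and 2 to 8 points at 50%. There only the age grouping matters.
- The planned Cox model may already use continuous age, and age group is offered only as an example.
- The assumed effects are strong. HR 2 per SD means a fourfold hazard between patients one SD below and one SD above the mean age, and odds ratio 3 means ninefold odds. At HR 1.5 the better test still reaches only 17 to 32%.

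These narrow the point but do not remove it. The univariate methods actually named group age and score toxicity as a proportion, and no continuous or ordinal analysis is committed to. The gap also does not depend wholly on the any-grade reading: a grade ≥ 3 table has 23 to 34% power, against 69 to 74%.

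**Conclusion.** The point holds in limited form. Grouping age costs about 36% of the trend information with a median split and 14 to 21% with three or four equal groups, assuming normal age and a linear effect. In toxicity tables that also halve age, the loss passes half at an any-side-effect rate somewhere between 50% and 70%. That depends on a definition and a rate the documents do not supply, so it is a possibility and not a finding. For recurrence, continuous age gains about 15 to 21 points at an assumed HR of 2 per SD and 4 to 11 at 1.5.

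These comparisons are secondary or exploratory, and no stopping rule or primary conclusion uses them. This is a worthwhile refinement, not a threat to the trial.

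**What to change.** Change Section 10.2 and the Study Summary as follows.

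1. Test age as a continuous variable by the score test in a univariable Cox model. State that age is also continuous in the multivariable Cox model. Keep grouped Kaplan-Meier curves for display, with the groups fixed in advance.
2. In all treated patients (about 32), relate worst CTCAE grade per patient (0 if none) to age by a Spearman rank trend test, and to nominal characteristics by exact Wilcoxon or Kruskal-Wallis tests. Keep incidence tables of treatment-related and serious events as description.
3. Label any per-toxicity tests exploratory and unadjusted for multiplicity.

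Section 6.3 refers to modified criteria for hematologic events in an unnamed appendix, while Section 7.0 uses CTCAE throughout. State one grading scale before worst grade is used.

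The cost is wording and a few lines of code, with no new data. The trend tests assume a roughly monotone age effect, which the retained grouped displays let a reader check. Worst overall grade also pools unlike toxicities, such as neutropenia and diarrhea. If the sponsor prefers to keep the tables as the test, the minimum is to fix the age cut points and the grade threshold now.

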Resistance to endocrine therapy in patients with HR+ Metastatic breast cancer is a major cause of treatment failure. Cyclin-dependent kinases 4 and 6 (CDK 4 and 6) inhibition is proving to be an effective strategy in overcoming endocrine resistance. The data on the use of CDK 4/6 inhibitors with Fulvestrant or an Aromatase Inhibitor has been discussed in section 1.1 and 1.2. However, patients will eventually become resistant to CDK 4/6 inhibitors. Other than ER positivity, we do not fully understand the mechanism of sensitivity or resistance to CDK 4/6 inhibitors in ER+ MBC apart from Rb (Retinoblastoma gene) loss predicting for resistance. However, rather than waiting for endocrine resistance to develop in the adjuvant or the metastatic setting, identifying and targeting endocrine resistance in the Neo-adjuvant setting is expected to delay or prevent the development of endocrine resistance and hence improve patient outcomes. The concept for this proposal originated from real patient scenarios. We identified three patients in our institution that developed localized non-metastatic HR+ recurrent breast cancer while on adjuvant Anastrozole.

All three were treated with NACT and none achieved a complete pCR. Molecular analysis of the recurrent tissue harbored CCND1 amplification and ctDNA analysis showed ESR1 mutations in all of the three patients. Besides Estrogen receptor positivity, CCND1 amplification is one suggested biomarker that could predict response to CDK 4/6 inhibitors. Furthermore, the PALOMA studies showed that Fulvestrant is effective in patients with ESR1 mutation. We then hypothesized this cohort of patients with the

CONFIDENTIAL

This material is the property of the [UC Irvine Chao Family Comprehensive Cancer Center](#). Do not disclose or use except as authorized in writing by the study sponsor.

aforementioned genomic changes will benefit from a combination of a CDK 4/6 inhibitor and Fulvestrant.

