2.3 Correlative Objectives

- 2.3.1 To determine if genomic analysis of patient matched breast tissue samples and serial mutational tracking of circulating tumor DNA can identify new mechanisms of endocrine resistance and how Abemaciclib overcomes endocrine resistance
- 2.3.2 To determine the mechanism of response or resistance to Abemaciclib
- 2.3.3 To determine biomarkers related to the Rb pathway

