3.1 Inclusion Criteria

- 3.1.1 Patients must have a diagnosis of HR+ breast cancer. To fulfill the requirement of HR+ disease, a breast cancer must express, by immunohistochemistry (IHC), at least one of the hormone receptors (ER, progesterone receptor [PgR]) as defined in the relevant American Society of Clinical Oncology (ASCO)/College of American Pathologists (CAP) Guidelines (Hammond et al. 2010):
 - For ER and PgR assays to be considered positive, $\geq 1\%$ of tumor cell nuclei must be immunoreactive by immunohistochemistry (IHC) (Hammond et al. 2010).
- 3.1.2 Patients must have Loco regional breast cancer (Stage I, Stage II and stage III per AJCC 8th edition criteria for staging of breast cancer)
- 3.1.3 Patients must have localized recurrence while on adjuvant endocrine therapy
- 3.1.4 Patients must have any known molecular evidence of endocrine resistance by next generation sequencing
- 3.1.5 Age ≥ 18 years.
- 3.1.6 ECOG performance status 0-1
- 3.1.7 Have post-menopausal status as defined by following:
 - Prior bilateral oophorectomy
 - Age ≥ 60 years
 - Age < 60 and amenorrheic (non-treatment-induced amenorrhea secondary to tamoxifen, toremifene, ovarian suppression, or chemotherapy) for at least 12 months. Follicle-stimulating hormone (FSH) and estradiol must be in the postmenopausal range.
- 3.1.8 Have at least one measurable disease as defined per RECIST 1.1
- 3.1.9 Adequate organ and marrow function as defined below:
 - Hemoglobin* > 8 g/dL
 - Absolute neutrophil count $\geq 1,500/\text{mcL}$
 - Platelets $\geq 100,000/\text{mcL}$
 - Total bilirubin $\leq 1.5 \times$ institutional ULN

Patients with Gilbert's syndrome with a total bilirubin ≤ 2.0 times ULN and direct bilirubin within normal limits are permitted

 - AST (SGOT)/ALT (SPGT) $\leq 2.5 \times$ institutional ULN
 - Creatinine $\leq 1.5 \times$ institutional ULN

**Patients may receive transfusion of packed red blood cells (PRBC) to achieve this hemoglobin level at the discretion of the investigator; however, initial study drug treatment must not begin earlier than the day after the PRBC transfusion.*

CONFIDENTIAL

This material is the property of the [UC Irvine Chao Family Comprehensive Cancer Center](#). Do not disclose or use except as authorized in writing by the study sponsor.

- 3.1.10 Able to swallow oral medications

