- 3.1.11 Patients who received adjuvant radiotherapy must have completed and fully recovered from the acute effects of radiotherapy. A washout period of at least 14 days is required between end of radiotherapy and screening for the study.
- 3.1.12 Patients who received chemotherapy must have recovered (Common Terminology Criteria for Adverse Events [CTCAE] Grade ≤1) from the acute effects of chemotherapy except for residual alopecia or Grade 2 peripheral neuropathy prior to enrollment. A washout period of at least 21 days is required between last chemotherapy dose and enrollment (provided the patient did not receive radiotherapy).
- 3.1.13 Any known markers of response or resistance to CDK 4/6 inhibitors to be present in the biopsy specimen
- 3.1.14 If patients have been treated with prior Neo-Adjuvant chemotherapy at the time of primary diagnosis and not at the time of recurrence, they will be included in the study.
- 3.1.15 Must be able to sign a written informed consent, are reliable, willing to be available for the duration of the study and are willing to follow study procedures

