3.2 Exclusion Criteria

- 3.2.1 Stage IV metastatic breast cancer
 - This study will utilize the American Joint Committee on Cancer (AJCC) staging system, eight edition that provides a strategy for grouping patients with respect to prognosis. The AJCC has designated staging by TNM classification. The researchers will also review tumor size, lymph node status, and estrogen-receptor and progesterone-receptor levels in the tumor tissue.
- 3.2.2 Patients with HER2 positive and triple negative breast cancer
 - To fulfill the requirement of HER2- and Triple negative disease, a breast cancer must not demonstrate, at initial diagnosis or upon subsequent biopsy, overexpression of HER2 or should not express ER or PR receptors by either IHC or in-situ hybridization (ISH) as defined in the relevant ASCO/CAP guidelines (Wolff et al. 2013).
- 3.2.3 Inflammatory breast cancer
- 3.2.4 Newly diagnosed endocrine naïve patients
- 3.2.5 No molecular evidence of endocrine resistance
- 3.2.6 Prior treatment with any CDK 4/6 inhibitor and/or Fulvestrant
- 3.2.7 Pre-menopausal women
- 3.2.8 Are currently receiving an investigational drug in a clinical trial or participating in any other type of medical research judged not to be scientifically or medically

CONFIDENTIAL

This material is the property of the [UC Irvine Chao Family Comprehensive Cancer Center](#). Do not disclose or use except as authorized in writing by the study sponsor.

compatible with this study. If a patient is currently enrolled in a clinical trial involving non-approved use of a device, then agreement with the principal investigator is required to establish eligibility

- 3.2.9 Have had major surgery within 14 days prior to enrollment to allow for post-operative healing of the surgical wound
- 3.2.10 Have initiated bisphosphonates or approved RANK ligand therapy for breast cancer with osseous metastasis, if patients are received Zolendronic acid or Denosumab in the adjuvant manner then such patients will be allowed participate
- 3.2.11 Have serious preexisting medical conditions that, in the judgment of the investigator, would preclude participation in this study (for example, history of major surgical resection involving the stomach or small bowel or preexisting Crohn's disease or ulcerative colitis, interstitial lung disease, severe dyspnea at rest, any pre-existing chronic condition resulting in baseline grade 2 or higher diarrhea)

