9.0 CORRELATIVE STUDY

Molecular analysis in the form of Next Generation Sequencing (NGS) will be performed on the treatment naïve archival breast tissue, on the breast tissue at the time of recurrence and on the surgical specimen. Blood will be collected as well for analysis of ctDNA before enrollment, every 3 months while on the treatment and then every 6 months (after definitive surgery) until the end of the study at five years. The molecular analysis by NGS will be done by Tempus using their standard platform.

Correlative Study Objective:

1. To determine if genomic analysis of patient matched breast tissue samples and serial mutational tracking of ctDNA can identify new mechanisms of endocrine resistance and the way Abemaciclib overcomes endocrine resistance
2. To determine the mechanism of response or resistance to Abemaciclib
3. To determine biomarkers related to the Rb pathway

Collection of tumor samples (archival, at time of recurrence, and from surgery) and ctDNA blood are mandatory.

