
CONFIDENTIAL

This material is the property of the UC Irvine Chao Family Comprehensive Cancer Center. Do not disclose or use except as authorized in writing by the study sponsor.

Abemaciclib overcomes endocrine resistance. For the analyses with matched pair tissue data we will use paired t tests or Wilcoxon sign rank statistical analysis in order to test differences in recurrent and treated breast tissue. We plan to measure absolute values and changes in circulating tumor DNA and correlate them with endocrine resistance. If serial monitoring of ctDNA can provide markers of resistance, we will quantify endocrine resistance as a composite outcome that will be quantified as dichotomous variable if it happens (yes or no) and at what time interval during our study. We will start our analysis by using frequency table analysis in order to examine the relationship between resistance or sensitivity and specific mutations.

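### Markers used for entry should not be tested for change from recurrent to treated tissue: selection biases that change toward apparent loss

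*Combined protocol and SAP*

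**What the plan says.** **Entry.** Section 3.1.4 states: "Patients must have any known molecular evidence of endocrine resistance by next generation sequencing". Section 3.2.5 excludes the complement: "No molecular evidence of endocrine resistance". Neither names the specimen to be sequenced. Section 3.1.13 does name one, for a different kind of marker: "Any known markers of response or resistance to CDK 4/6 inhibitors to be present in the biopsy specimen".

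**Specimens.** Section 9.0 sequences the archival treatment-naive tissue as well, and then DNA "on the breast tissue at the time of recurrence and on the surgical specimen". It adds: "Collection of tumor samples (archival, at time of recurrence, and from surgery) and ctDNA blood are mandatory". No second recurrence sample is planned.

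**Analysis.** For matched tissue, section 10.2 says "we will use paired t tests or Wilcoxon sign rank statistical analysis in order to test differences in recurrent and treated breast tissue", and the synopsis says the same in substance. The variable, the alpha level and the sidedness are not stated. For specific mutations, 10.2 also plans frequency tables. The comparison serves objective 2.3.1, which asks whether the genomic data "can identify new mechanisms of endocrine resistance and how Abemaciclib overcomes endocrine resistance".

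**Design and status.** Section 10.1 describes an open-label, single-centre phase II trial and mentions no comparator. Section 10.2 acknowledges low power for secondary and exploratory endpoints.

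**The concern.** A patient enters because a marker was found. If the same tissue then serves as the first half of a before-and-after comparison, the baseline value of that marker has been selected to be positive, or high. For a present/absent result, a miss at surgery through sampling, low cellularity or assay sensitivity counts as a loss, and no gain can offset it. For a quantitative level, patients can move either way, but the average drifts down because the baseline was selected high.

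With no control arm and no independent baseline sample, the test cannot separate this drift from a drug effect. Objective 2.3.1 is worded around resistance being overcome, so a significant fall would invite that reading.

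**Working it through.** **Plan's own figure.** None is given for the paired tissue tests. The figures for the primary pCR design (10 then 29 patients, r1 = 1, r2 = 5) reproduce by exact two-stage binomial: type I error 0.0471, power 0.8051, early stopping 0.7361, expected size 15.0. They do not depend on the tissue analysis.

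**Inputs**
- All patients positive at baseline: follows from 3.1.4, 3.2.5 and 3.1.13, if the recurrence tissue gave the qualifying result.
- Number of pairs n = 25: assumed. The design has 29 evaluable patients, and a pCR leaves no invasive tumor at the primary site to sequence. At the design's pCR rates of 10% and 30%, 29 × 0.9 ≈ 26 and 29 × 0.7 ≈ 20 pairs remain.
- Miss rate q at surgery for an unchanged marker: not in the documents; 2% to 20% assumed.
- Two-sided 0.05: assumed.

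**Step 1: losses needed for significance.** With k losses, no gains and n pairs coded −1 or 0, the paired t statistic has absolute value √[k(n − 1)/(n − k)].
- k = 3: √(3 × 24/22) = 1.81, p = 0.083.
- k = 4: √(4 × 24/21) = 2.14, p = 0.043.

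So 4 losses suffice. The Wilcoxon test by normal approximation gives z = √k = 2 at k = 4, p = 0.046, the same threshold. An exact sign test gives 2 × 0.5^k: 0.0625 at k = 5 and 0.031 at k = 6, so it needs 6.

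**Step 2: chance of reaching it with no drug effect.** Losses K follow Binomial(25, q).

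| Assumed miss rate q | Expected losses | Paired t, P(K ≥ 4) | Exact, P(K ≥ 6) |
|---|---|---|---|
| 2% | 0.5 | 0.001 | <0.001 |
| 5% | 1.25 | 0.034 | 0.001 |
| 10% | 2.5 | 0.24 | 0.03 |
| 20% | 5.0 | 0.77 | 0.38 |

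The threshold stays at 4 for n = 20 and n = 29. At q = 10% the paired t result is 0.13 with 20 pairs and 0.33 with 29; at q = 5% it is 0.016 and 0.055.

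**Step 3: quantitative marker.** A simulation of 20,000 trials with n = 29 and no drug effect selected the baseline above a cut-off passed by 54% or 11% of patients. These are the ends of the ESR1 range in 10.2, used here only to set how strict the selection is. Test-retest correlations are assumed.

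| Correlation | Rejection rate, 54% | Rejection rate, 11% |
|---|---|---|
| 0.95 | 0.09 | 0.29 |
| 0.90 | 0.14 | 0.52 |
| 0.80 | 0.24 | 0.83 |
| 0.50 | 0.55 | 0.999 |

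In these runs 17% to 45% of patients still rise, so the bias is in the mean and not in every patient.

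**Step 4: does removing the selection cure it?** With a continuous marker not used for entry, the simulated rejection rate at n = 29 is about 0.05 at every correlation tried. Changing only to an exact test does not remove the bias: Step 2 still shows 0.38 at q = 20%.

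**The case against.** The strongest counter-argument is that the documents do not tie the endocrine-resistance result to the biopsy. Section 3.1.4 names no specimen, and in the motivating cases of section 1.4, "Molecular analysis of the recurrent tissue harbored CCND1 amplification and ctDNA analysis showed ESR1 mutations in all of the three patients". Only 3.1.13 names the biopsy, and it concerns CDK 4/6 markers. If ctDNA qualified the patient, the tissue baseline is selected only indirectly and the bias is smaller. This stands, and it is why the point is conditional.

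Second, 10.2 names no variable. The modelled test, one yes/no marker positive in every pair, is a construction. Patients may qualify on different alterations: if one alteration qualified only 12 patients and were tested in those 12, 4 losses are still needed and the paired t rejection rate at q = 10% is 0.026. This stands as a limit on size.

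Third, at miss rates of 5% or less the paired t test on 25 pairs stays below nominal. This also stands. The low power acknowledged in 10.2 does not answer the point, however, because the problem is bias toward a false positive.

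Stronger readings are tempting and not supported:
- *All change must be loss.* True only for present/absent status of a qualifying marker. Quantitative levels and non-qualifying alterations can rise.
- *The trial will wrongly claim that resistance was overcome.* No criterion for that is set in 10.2, and loss of a CDK 4/6 marker would not by itself show it.
- *The archival tissue goes unused.* It is sequenced and falls within the planned analysis of matched samples. What is missing is a named summary for the archival-to-recurrence pair.

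**Conclusion.** The point holds in conditional form. Where the recurrence tissue supplied the qualifying result, a paired test of that marker against the surgical specimen is biased toward loss, and the design has nothing to correct it.

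The bias ranges from negligible at a 2% miss rate to serious at 10% or more by paired t test. An exact test is below nominal at 10% and well above it at 20%. All of these rest on 25 pairs, a single binary marker positive in every pair, no drug effect and two-sided 0.05. The miss rate is an assumption throughout, so no single figure can be called this trial's error rate.

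The analysis is exploratory. It does not affect the pCR decision rule. I rate it minor, but worth correcting before the tissue data are read.

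**What to change.** In section 10.2:
1. Exclude the markers that qualified a patient from the recurrent-versus-treated hypothesis tests. Report them descriptively as retained or not detected at surgery, with an exact confidence interval, and state for each patient which specimen (recurrence tissue or ctDNA) gave the qualifying result.
2. Limit the paired tests to features not used for entry, and count gains and losses together. Testing only alterations that are new at surgery would build in the opposite bias, because those can only be gained.
3. Optionally, summarise the archival-to-recurrence pair descriptively. A miss in archival tissue would look like acquisition, so this pair should not be tested or presented as proof of acquired resistance.

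The cost is wording, plus recording the qualifying specimen; no new samples are needed. The downside is fewer p-values to report.
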